### **12.4.3 Pharmacodynamics**

Change from baseline in CXCL9, IL-1, IL-6, sIL-2R and any other selected biomarkers relevant for hyperinflammation that are collected, will be summarized with descriptive statistics by visit.

## 13 Safety analyses

In addition to the summaries of safety data for the CSR presented in subsequent sections, listings and tabulations may be provided ad-hoc for the SRC to support their review, as appropriate, in addition to individual case reports etc. from the study centres. Further details will be provided in the SRC charter.

### 13.1 Adverse events

All AEs will be coded using MedDRA version 21.1.

A treatment-emergent AE (TEAE) is defined as an AE with a start date/time after randomization.

The number and percentage of patients with at least one TEAE, at least one serious TEAE, including death, at least one non-serious TEAE, any related TEAE, any fatal TEAE, any TEAE leading to study treatment withdrawn and any TEAE leading to study withdrawal will be summarized.

The number and percentage of patients with at least one TEAE will be summarized in frequency tables by treatment, system organ class and preferred term. Separate tables will present TEAEs classified by relationship to study treatment or to standard of care and TEAEs classified by maximum severity. These tables will be presented by PT in descending order of frequency across all groups. Percentages will be based on the number of patients in the All Treated population for the specific treatment group.

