5.4.7 Concomitant therapy

5.4.7.1 Prophylactic therapy

For patients randomized to emapalumab, prophylaxis for Herpes Zoster virus infection has to be in place from the day before initiation of emapalumab treatment until end of study.

Version 7.0 Final Protocol, Date 24 Jun 2020

The prophylactic therapy will be recorded in the CRF.

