5.5.1.3 Visit 1, Baseline (Day 1)

Once all inclusion and exclusion criteria have been reviewed and recorded, and the patient has been found eligible, the patient will be randomized into one of the treatment groups and the first dose of study drug will be administered accordingly (see Section 5.4.5). Please refer to Table 2 for other clinical and laboratory parameters to be collected during the visit.

During the treatment period (Days 1 to 15), clinical and laboratory assessments and procedures should preferably be performed before IMP administration.

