### 8.2.2 Imputation of adverse event start dates

To assess if AEs are treatment emergent, missing onset dates will be imputed according to the following rules:

- If day is missing and month and year of AE onset is the same as the month and year of first dose of study treatment (or date of randomization for patients on standard of care), then the onset date of the AE will be assumed to be the same as the date of first dose of study treatment (or date of randomization for patients on standard of care).
- If day and month is missing and year of AE onset is the same as year of first dose, then the date of onset will be assumed to be the same as the first dose of study treatment (or date of randomization for patients on standard of care).
- Otherwise, if day is missing, then use YYYY-MM-01, and if day and month are missing, then use YYYY-JAN-01.
- Completely missing onset dates will not be imputed. AEs with a completely missing onset date will be considered treatment-emergent.

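### The SAP counts only AEs that start after randomization, but imputes partial onset dates to the randomization date (SoC) or first-dose date (active arms), so read literally it excludes events the imputation is meant to include

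*SAP*

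**What the plan says.** SAP 13.1 gives the rule that feeds the adverse event tables: "A treatment-emergent AE (TEAE) is defined as an AE with a start date/time after randomization". It does not say what happens when onset falls on the randomization date itself, or when the time is missing.

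SAP 8.2.2 opens with its purpose: "To assess if AEs are treatment emergent, missing onset dates will be imputed according to the following rules". Its rules are:

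- Day missing, same month and year as first dose: "then the onset date of the AE will be assumed to be the same as the date of first dose of study treatment". For SoC the randomization date is used instead.
- Day and month missing, same year as first dose: "then the date of onset will be assumed to be the same as the first dose of study treatment", again with the randomization date for SoC.
- Other partial dates: "Otherwise, if day is missing, then use YYYY-MM-01, and if day and month are missing, then use YYYY-JAN-01".
- No date at all: "AEs with a completely missing onset date will be considered treatment-emergent".

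No rule imputes a time of day.

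Protocol 5.5.1.3 puts randomization and first dose in the same visit. Once eligibility is confirmed, "the patient will be randomized into one of the treatment groups and the first dose of study drug will be administered accordingly".

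**The concern.** The two SAP sections do not fit together. Section 8.2.2 exists to resolve doubtful onset dates, and its treatment of wholly undated events shows that it leans towards inclusion. Section 13.1 then applies a strict *after*, which an onset placed on the randomization date cannot meet. The result is perverse: an event known to have occurred in the start month is dropped, while an event about which nothing is known is kept.

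A related gap concerns Day 1 events with a full date and no time. Reactions to the first infusion fall here. Infusion related reactions are a safety endpoint (SAP 3.4.3), and severe ones are tabulated for the emapalumab group (SAP 13.1.3).

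What is at stake is the count in the TEAE tables: the overview and frequency tables in 13.1, serious TEAEs in 13.1.1, TEAEs leading to study withdrawal in 13.1.2 and events of special interest in 13.1.3. The primary efficacy analysis is not touched.

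**Working it through.** The plan gives no figure to reproduce, so the check applies the 8.2.2 rules to test cases and compares each result with the randomization date.

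**Inputs.** The TEAE rule is from SAP 13.1, the imputation rules from SAP 8.2.2, the Day 1 sequence from Protocol 5.5.1.3, and 18 patients per arm from SAP 6. For illustration, randomization is set at 10 July 2020. The anchor date is 10 July for SoC, 10 July for an active-arm patient dosed the same day, and 11 July for one dosed the next day.

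**Test.** The event is a TEAE if the imputed date > randomization date, compared by date because no time is imputed.

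| Onset as recorded | SoC | Active, dosed same day | Active, dosed next day |
|---|---|---|---|
| Day missing, July 2020 | 10 July: no | 10 July: no | 11 July: yes |
| Day and month missing, 2020 | 10 July: no | 10 July: no | 11 July: yes |
| Full date equal to the anchor date, no time | 10 July: no | 10 July: no | 11 July: yes |
| Day missing, August 2020 | 1 Aug: yes | 1 Aug: yes | 1 Aug: yes |
| Day missing, June 2020 | 1 June: no | 1 June: no | 1 June: no |
| Completely missing | yes (by rule) | yes (by rule) | yes (by rule) |

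**Reading the table.**

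1. The first two rows are the conflict. In SoC it is unconditional, because the imputed date is the randomization date. In an active arm it depends on the first dose falling on the randomization date, which is the scheduled case.
2. The third row is a gap, not a stated exclusion. It gives *no* only if the comparison is made on dates alone.
3. The August and June rows behave sensibly. Partial dates outside the start month, where the month is known, are not part of the problem.
4. The last row shows the reversal: no date counts, a known month does not.

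**With >= in place of >.** The first three rows become *yes* in all three columns. The June row stays *no*, and the August and undated rows stay *yes*.

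**Size per patient.** 1/18 = 0.0556, so one patient gained or lost moves an arm's incidence by 5.6 percentage points. The documents give no rate of partial or untimed onsets, so the total cannot be computed.

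**The case against.** Several arguments limit the point.

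*The intent is plain, so a programmer would include these events.* The stated purpose of 8.2.2 supports that. Its second rule also sets onset to the first dose rather than only to its date, and the first dose follows randomization, so in the active arms that rule can be read as satisfying 13.1. This holds for that rule. It does not rescue the first rule, which names a date, and it does nothing for SoC. In an open-label trial the handling should be written down, not left to whoever programs the tables.

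*The SAP does not exclude untimed Day 1 events.* Correct. A reader might infer that all such events, first-infusion reactions included, fail the definition. The documents do not support that. Section 13.1 speaks of date and time, so a reaction with a recorded time after randomization counts. Protocol 5.5.4.1.2 mentions only an onset date and the SAE listing in SAP 13.1.1 only start and stop dates, but the CRF is not available, so whether AE times are captured is unknown.

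*Few events will be affected, and serious ones are not hidden.* This largely stands. Patients enter with respiratory distress and are mostly in hospital, AE collection is restricted (Protocol 5.5.4.3.1), and an unknown onset day should be uncommon. SAEs are listed without restriction to TEAEs (SAP 13.1.1), and deaths are listed with them (13.1.4).

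*The loss differs by arm.* A reader might infer a bias between arms. It is possible: if an active-arm patient is dosed on a later date, the imputed event counts, while its SoC equivalent cannot. The prophylaxis rule makes a later first emapalumab dose plausible, since "prophylaxis for Herpes Zoster virus infection has to be in place from the day before initiation of emapalumab treatment until end of study". But the documents do not show how often this happens, and no formal comparison of AE rates is planned.

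*The active arms should be counted from first dose.* A reader might infer this from 8.2.2, or from Protocol 5.5.4.1.1, which ties treatment-emergence to use of study treatment. A common randomization anchor is defensible with an untreated control. With mixed anchors, any interval between randomization and dosing would count only in SoC, which creates an asymmetry.

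**Conclusion.** The inconsistency is real and is in the text. Taken literally, 13.1 and 8.2.2 together remove from the TEAE tables every SoC event with a partial date in the start month (or start year, if the month is also missing), and the same events in the active arms when dosing is on the randomization date. That is the opposite of what 8.2.2 is for. For untimed Day 1 events the fault is a missing rule: a strict comparison at date level would omit them, but the SAP does not require one.

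The reach is limited. The number of affected patients is unknown and probably small, and the documents give no basis for an upper bound. The only supportable figure is 5.6 percentage points per affected patient, assuming 18 patients in the arm's safety population. The conclusion also assumes that imputed onsets are compared by date and, for the active arms, that the first dose falls on the day of randomization. The change is worth making because it is cheap and affects the definition behind the TEAE tables, not because a large distortion has been shown.

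**What to change.** In SAP 13.1, define a TEAE as an AE with start date/time on or after randomization, in all arms. Add that where the time is missing or the date is imputed, an event on the randomization date counts as treatment-emergent, and that a recorded time before randomization excludes it. Section 8.2.2 can stay as it is, since its imputed dates then give the intended result in every arm.

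The cost is one sentence and a small programming change, with no new data to collect. The downside is that an untimed Day 1 event that began before randomization or dosing may be counted. That agrees with the inclusive approach 8.2.2 already takes to undated events. For SAEs the risk is small in the active arms, because Protocol 5.5.4.3.2 requires reporting of those that occur after study drug initiation.

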#### 13.1.1 Serious adverse events

The number and percentage of patients with at least one serious TEAE will be tabulated by SOC and PT. SAEs will also be listed. The listing will include information on treatment group, age, sex, race, start/stop date of event, SOC/PT, causality, severity, action taken, and outcome.

#### 13.1.2 Adverse events leading to withdrawal

The number and percentage of patients with TEAEs leading to study withdrawal will be presented by SOC and PT.

#### 13.1.3 Adverse events of special interest

The number and percentage of patients with treatment emergent adverse events of special interest will be presented:

- Emapalumab treatment group: Infections caused by pathogens potentially favored by IFN- $\gamma$  neutralizations such as mycobacteria, salmonella, shigella, herpes zoster and histoplasma capsulatum, and severe infusion-related reactions.
- Anakinra treatment group: Severe neutropenia.

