4.2.1 Secondary endpoints supporting the secondary objective

Safety endpoints of this study are:

- Treatment-emergent serious adverse events (SAEs).
- Adverse events leading to premature discontinuation of study treatment.
- Infusion related reactions including anaphylactic/anaphylactoid reactions.
- Treatment emergent adverse events of special interest:
 - Emapalumab treatment group: All new infections.
 - Anakinra treatment group: Severe neutropenia.
- Treatment-emergent laboratory abnormalities.

- Presence of anti-drug antibodies (ADAs) and neutralizing antibodies (Nabs) against emapalumab and anakinra.
- •

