5.5.4.3 Reporting requirement of adverse events

5.5.4.3.1 Reporting of adverse events

Irrespective of seriousness, the following adverse events are considered as adverse events of special interest and must be reported on AE page of the CRF.

In all patients:

• AEs leading to discontinuation of study treatment

Infusion related reactions including anaphylactic/anaphylactoid reactions. In patients treated with emapalumab, the following AEs will be considered of special interest:

• All new infections.

In patients treated with anakinra, the following AEs will be considered of special interest:

• Severe neutropenia defined as neutrophil count $< 0.5 \times 10^{9}$ /l.

No other AEs are required to be reported on the AE page of the CRF

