5.5.4.13 Specific safety monitoring and management during the study

Infusion related reactions for all treatment arms:

The infusion related reactions will be closely monitored by the treating physician. Should severe allergic reactions (such as anaphylactic shock) occur, the patient would be managed according to the local standard treatment guidelines.

Anakinra treatment:

• Neutrophil counts should be assessed prior to initiating and during anakinra treatment. Should neutropenia (neutrophil count < $1.0 \times 10^{9}/L$) occur in a patient treated with anakinra, dose reduction or discontinuation of the treatment may be considered as judged by the investigator. Should neutropenia (neutrophil count < $0.5 \times 10^{9}/L$) occur in a patient treated with anakinra, the treatment should be discontinued.

• Anakinra is mainly eliminated by the kidney. Should severe renal impairment (CLcr < 30 ml/min) or end stage renal disease occur, the reduction of anakinra dose (100mg IV 2 times daily) should be considered as judged by the investigator.

Emapalumab treatment:

Monitoring of new infections is requested throughout the study. Type of investigation, specimen, result and pathogen identified will be captured in the CRF. Such data will be captured for all new infection. Should serious infection caused by pathogens potentially favored by IFNγ neutralization, i.e. mycobacteria, histoplasma capsulatum, herpes zoster, salmonella and shigella occur in a patient treated with emapalumab, the treatment should be stopped, and appropriate anti-infective treatment should be initiated.

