### 3.4.3 Safety endpoints

Safety endpoints of this study are:

- Treatment-emergent serious adverse events (SAEs).
- Adverse events leading to premature discontinuation of study treatment.
- Infusion related reactions including anaphylactic/anaphylactoid reactions.
- Treatment emergent adverse events of special interest:
  - Emapalumab treatment group: All new infections.
  - Anakinra treatment group: Severe neutropenia.
- Treatment-emergent laboratory abnormalities.
- Presence of anti-drug antibodies (ADAs) against emapalumab and anakinra, and presence of neutralizing antibodies (Nabs) against anakinra.

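### SAP 13.1.3 does not report new infections and infusion-related reactions as SAP 3.4.3 and the protocol define them

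*SAP*

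**What the plan says.** **Endpoints.** SAP 3.4.3 gives the special-interest infection endpoint as "Emapalumab treatment group: All new infections". Protocol 4.2.1 says the same. Both sections also list, as a separate safety endpoint, "Infusion related reactions including anaphylactic/anaphylactoid reactions", with no restriction by severity or by arm.

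**Reporting rule.** Protocol 5.5.4.3.1 makes both of them events of special interest, to be entered on the AE page whether or not they are serious. Infusion reactions come under the heading for all patients, before the arm-specific lists begin: "Infusion related reactions including anaphylactic/anaphylactoid reactions. In patients treated with emapalumab, the following AEs will be considered of special interest". The emapalumab list then has the entry "All new infections".

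**Monitoring.** Protocol 5.5.4.13 opens with "Infusion related reactions for all treatment arms". For emapalumab it asks for the investigation, specimen, result and pathogen of each infection, adding "Such data will be captured for all new infection".

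**Analysis.** SAP 13.1.3 is the section that summarises special-interest events. Its emapalumab entry starts with "Infections caused by pathogens potentially favored by" IFN-gamma neutralization, gives example organisms, and ends "herpes zoster and histoplasma capsulatum, and severe infusion-related reactions". Its anakinra entry contains severe neutropenia and nothing else.

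**The concern.** Safety and tolerability form the trial's secondary objective, and these are two of its named endpoints. A programmer who follows SAP 13.1.3 exactly will produce counts for a subset of each endpoint. A reader of the study report could then take the special-interest table as the result for the endpoints in SAP 3.4.3.

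The restricted AE collection adds weight. Apart from serious events, Protocol 5.5.4.3.1 requires only special-interest events on the AE page. Non-serious infections under emapalumab and non-serious infusion reactions are therefore collected largely because they were declared of special interest. The special-interest summary is where a reader would look for them, and many would not be there.

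**Working it through.** No rate, power or error level enters this point, and the plan gives no figure to reproduce. The check is a comparison of texts.

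| | Endpoint and reporting rule (Protocol 4.2.1, 5.5.4.3.1; SAP 3.4.3) | Analysis (SAP 13.1.3) |
|---|---|---|
| Infections: which | All new infections | Those from pathogens potentially favoured by IFN-gamma neutralization |
| Infections: arm | Emapalumab | Emapalumab |
| Infusion reactions: severity | No limit stated; anaphylactic/anaphylactoid reactions included | Severe only |
| Infusion reactions: arm | No limit in the endpoint; all patients in Protocol 5.5.4.3.1 | Emapalumab only |
| Severe neutropenia | Anakinra | Anakinra |

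1. **Infections.** The arm matches and the scope does not. The organisms named in 13.1.3 are introduced as examples, so the list is open. The category is still narrower than all new infections.

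2. **Infusion reactions.** Both severity and arm differ. Under Protocol 5.4.5.2 anakinra is also given by intravenous infusion. If the full schedule is given, that is 4 per day × 15 days = 60 infusions per patient, against 5 for emapalumab. The arm with more infusions has no infusion-reaction entry.

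3. **Is the endpoint reported elsewhere in the SAP?**
   - SAP 13.1 counts patients with treatment-emergent events by treatment, system organ class and preferred term, with further tables by relationship and by maximum severity. SAP 13.1.1 tabulates and lists serious events. All reported events therefore appear somewhere.
   - For infections, a class-level row would come close to the endpoint, because a treatment-emergent event must start after randomization. It need not be identical: Protocol 5.5.4.1.1 also counts exacerbation of a pre-existing disease as an adverse event, which could bring in worsening of the underlying infection. The row is not labelled as the endpoint.
   - For infusion reactions there is no near-equivalent. The terms can fall under several classes. No SAP section says which terms make up an infusion-related reaction or counts patients with any such reaction in either infused arm.

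4. **Result.** SAP 13.1.3 disagrees with SAP 3.4.3 and with the protocol on both endpoints, and no other SAP section supplies either one as defined.

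**The case against.** The strongest reply is that this is a labelling problem in a descriptive table. Every reported event is in the general tables, serious infections are also listed patient by patient, and the safety review committee sees adverse events continuously and can be given ad hoc tabulations (SAP 13). No decision rule uses the 13.1.3 table. The narrower infection category also has a protocol basis: Protocol 5.5.4.13 singles out the same organisms. Finally, SAP 3.4.3 and Protocol 4.2.1 list infusion reactions apart from special-interest events and do not say all patients or any severity; the first comes from Protocol 5.5.4.3.1 and the second from the absence of a limit.

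Most of this stands. It limits the consequence, and it is a good reason to keep the pathogen group as a breakdown. It does not remove the contradiction between SAP 3.4.3 and 13.1.3, and it does not supply an infusion-reaction count.

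Some stronger readings are tempting, and the documents do not support them:
- *Other infections disappear from the report.* They do not; see SAP 13.1 and 13.1.1.
- *Only five named organisms count, so bacterial pneumonia, sepsis or line infection is excluded.* The organisms are examples, and inclusion depends on the pathogen and not on the site or syndrome.
- *The reported infection figure would be near zero.* No infection rate or pathogen distribution is given, and nothing presents 13.1.3 as the main infection result.
- *SAP 13.1.3 introduced the restriction of infections to emapalumab.* That restriction is already in the endpoint.

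**Conclusion.** The point holds as an inconsistency between defined endpoints and planned analysis. SAP 13.1.3 contradicts SAP 3.4.3 and Protocol 4.2.1 and 5.5.4.3.1, and followed as written it yields counts that are not the SAP's own safety endpoints. The gap is modest for infections, where a class row comes close. It is larger for infusion reactions, where no total exists and the anakinra arm has no entry.

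The difference between the defined and tabulated counts cannot be sized, because the documents give no expected rates for either event. The conclusion rests on reading an endpoint with no stated severity limit as covering all severities, and on the infusion-reaction line in Protocol 5.5.4.3.1 belonging to the heading for all patients, as its position shows. The primary analysis and the stopping rules are unaffected. The SAP should be corrected, but no information is at risk of being lost.

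**What to change.** Align SAP 13.1.3 with SAP 3.4.3 and Protocol 5.5.4.3.1 by reporting the number and percentage of patients with:

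1. any new infection in the emapalumab arm, with the IFN-gamma-related pathogens as a sub-row;
2. any infusion-related reaction in both infused arms, with severe and anaphylactic/anaphylactoid reactions as sub-rows;
3. severe neutropenia in the anakinra arm.

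Add a footnote to row 1: in the other arms a non-serious infection need not be reported unless it led to discontinuation of study treatment, so the row is descriptive and does not support a between-arm comparison. For row 2, state how an infusion-related reaction is identified, for example by the investigator's special-interest report or by a prespecified term list.

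The cost is a few lines of SAP text and a few table rows from data the protocol already collects. SAP 5.2 has the SAP signed before the Stage 1 interim, so if that has happened the change goes in as a SAP amendment. No visit, assessment or clinical procedure changes.
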